- If, on the other hand, the CMOG becomes aware of a “Stop Use” criterion during the telephone call that the participant did not identify, all Virtual Visit 2 procedures except a participant TASS and study mandated test for LDL-C will be performed. The reason for not repeating the TASS is that the participant did not self-identify the “Stop Use” criterion. Instead, the CMOG identified the criterion and discussed with the participant, which could bias the participant’s behavior when completing the TASS. For example, a participant who did not realize they should have stopped drug because of severe muscle symptoms, may answer “yes” to this question in the TASS and be categorized as a correct selector when, in reality, they may have answered “no” to this question if they had not spoken to a CMOG clinician prior to completing the TASS. Because the study staff had to

inform the participant that they met a “Stop Use” criterion, they will be considered a failure when evaluating the second co-primary endpoint related to “use”.

- Participants who the CMOG clinicians identify as having experienced “Stop Use” criteria are considered “Discontinued from Study Intervention” and not a withdrawal (refer to Section 7.1). In general, the only events recorded in an eDiary or communicated to the study staff during a phone check that would result in study medical personnel instructing the participant to stop taking rosuvastatin are “Stop Use” criteria. If such a situation occurs, the participant will be classified as a discontinuation from study intervention due to “Adverse Event” or “Pregnancy” and scheduled for a Virtual Visit 2.

If a participant records a “Do Not Use” warning in their eDiary, we will not contact them. Our intent in the AUS is to keep interactions with the participants to a minimum so we do not influence the participant’s behaviors or bias the outcome of the study. By doing this, we allow the real-life behavior to continue into the next reorder, at which time, the TASS reorder assessment would result in a “Crestor OTC is no longer right for you” message along with a message to stop drug and contact a doctor. In the AUS, the participant will also be messaged to contact the call center to schedule Virtual Visit 2.

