	AAD	Incorrect AAD	Correct AAD (CAAD +MCAAD)	Incorrect AAD	Incorrect Missing

The primary analysis for the Overall Correct Initial TASS Outcome will be reported as follows:

	Analysis Population (N=XXX)		
	N	%	95% CI
Overall Correct Initial TASS Outcome	XX	XX%	(LB%, UB%)
Correct Selectors	XX	XX%	(LB%, UB%)
Correct AAD	XX	XX%	(LB%, UB%)
MR _{ap}	XX	XX%	(LB%, UB%)
MR _{ps}	XX	XX%	(LB%, UB%)

where,

- Correct Selectors (Cs) = Obtain a correct TASS outcome that they qualify for Crestor OTC by receiving an 'OK to Use' screen in the TASS (compared to the CMOG clinician evaluation)
- Correct AAD (CAAD) = Obtain a correct TASS outcome that they must ask a doctor before qualifying for Crestor OTC by receiving an 'Ask a Doctor' screen in the TASS (compared to the CMOG clinician evaluation)
- MR_{ap} = Mitigated results *a priori*
- MR_{ps} = Mitigated results post-study (should there be any post-study mitigations).

The primary analysis of the first co-primary endpoint will be based on a worst case scenario missing data imputation where all participants in the respective analysis population with a missing CMOG clinician initial TASS outcome will be counted as Incorrect for the endpoint. An additional secondary analysis of this endpoint will be conducted based on the AUS ITT population. In addition to the worst case scenario analysis for the first co-primary endpoint, sensitivity analyses will be performed on the participants in the SS population with a non-missing initial TASS outcome for the CMOG clinician (i.e., complete case analysis) and with missing Overall Correct Initial TASS Outcome data imputed using best case imputation and a tipping point analysis. Further details for those participants (or CMOG clinician) with missing initial TASS outcomes and the sensitivity analyses will be described in the study SAP.

2 Percentage of participants with an Overall Correct (correct + mitigated) Final Use Outcome at the final use assessment, defined as the number of participants with a correct *final* use outcome divided by the number of participants in the analysis population with a non-missing final use outcome for both the participant and CMOG clinician (Threshold: 85% LB). This will be calculated as follows:

$$\text{Overall Correct Final Use Outcome (\%)} = \frac{C_S + C_{AAD} + C_R + M_{RAP} + M_{RPs}}{\text{\# of participants in the analysis population with a non-missing final use outcome for both the participant and CMOG clinician}}$$

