The above null hypothesis will be rejected in favor of the alternative if the lower bound of the two-sided 95% exact binomial (i.e., Clopper-Pearson) confidence interval is greater than 85%.

For the second co-primary endpoint, the Overall Correct Final Use Outcome at the final use assessment is computed as follows:

$$\text{Overall Correct Final Use Outcome (\%)} = \frac{C_S + C_{AAD} + C_{R} + M_{R_{AP}} + M_{R_{PS}}}{\text{Number of participants in the analysis population with a non-missing final use outcome for both the participant and CMOG}}$$

where:

- Correct Selector (CS) = Obtain a correct outcome that they qualify for Crestor OTC (compared to the CMOG evaluation)
- Correct AAD (CAAD) = Obtain a correct outcome that they must ask a doctor before qualifying for Crestor OTC (compared to CMOG evaluation)
- Correct Rejectors (CR) = Obtain a correct outcome that they do not qualify for Crestor OTC

(compared to CMOG evaluation)

- Mitigated results *a priori* (MR_{AP})
 - MC_S = Mitigated Correct Selector
 - MC_{AAD} = Mitigated Ask A Doctor
 - MC_R = Mitigated Correct Rejector
- Mitigated results post-study (MR_{PS})
 - MC_S = Mitigated Correct Selector
 - MC_{AAD} = Mitigated Ask A Doctor
 - MC_R = Mitigated Correct Rejector

Evaluation of the Overall Correct Final Use Outcome will have a sample size of at least 500 participants. A sample size of 500 participants would provide at least 90% power to demonstrate that the lower bound of the 95% exact binomial confidence interval is greater than 85% for the final use endpoint, assuming that the true correct final use outcome rate is 90%. That is, the sample size of 500 provides at least 90% power to test the following set of hypotheses for the primary endpoint on the final use outcome:

$$H_0: P \leq 85\% \text{ vs. } H_1: P > 85\%$$

where P is the proportion of Overall Correct Initial TASS Outcome or the proportion of Overall Correct Final Use Outcome, respectively.

The above null hypothesis will be rejected in favor of the alternative if the lower bound of the two-sided 95% exact binomial (i.e., Clopper-Pearson) confidence interval is greater than 85%.

The third co-primary endpoint is the percent change from baseline (PCFB) in verified LDL-C values to Visit 2 in participants regardless of their final use outcome. PCFB in verified LDL-C to Visit 2 is computed as follows:

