A participant may be discontinued from the study intervention by the CMOG at a scheduled follow-up phone call or eDiary review if the participant has not already identified the following conditions and stopped study drug: pregnancy; severe and unexplained muscle pain, tenderness or weakness; and symptoms of liver problems (upper belly pain, dark urine, yellowing of skin or whites of eyes). Note that discontinuation from study intervention is NOT the same thing as a withdrawal from the study. If such a situation occurs, the participant’s disposition will be classified as “Pregnancy” for this “Stop Use” warning or “Adverse Event” for severe and unexplained muscle pain, tenderness or weakness, or symptoms of liver problems. In these instances, the participant will be scheduled for a Virtual Visit 2 and all procedures will be performed except a final TASS assessment and a study mandated test (SMT) for LDL-C. In these situations, the final TASS assessment will be considered “Incorrect” since the participant did not identify the condition and stop medication. If the participant identifies the condition and stops medication on their own, they will be scheduled for Virtual Visit 2 and all procedures including the final TASS assessment will be performed.

The PP population includes participants that have completed the study. “Completed” means the participant completed the study if he/she has completed all phases of the study, including Virtual

Visit 2. “Completed” also includes participants that have discontinued with sufficient medical and medication history information and, when necessary, a verified LDL-C value collected prior to stopping the study in order to determine a final use outcome and has not withdrawn from the study. The goal is to have 100 limited literacy participants in the trial.

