4.1.3 Missing Data Conventions

All primary analyses, except the first co-primary endpoint, will be conducted based on a complete case analysis (i.e., observed data).

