 - MC_R = Mitigated Correct Rejector

The denominator for the primary analysis of the second co-primary endpoint will only include those participants in the analysis population with a non-missing final use outcome for the participant and CMOG. The target threshold for this endpoint is that the lower bound of the 95% exact confidence interval needs to be greater than 85% overall.

For the second co-primary endpoint, the PE of the Overall Correct Final Use Outcome, with *a priori* and post-study mitigations, will be reported with a two-sided 95% confidence interval which will be computed using exact binomial (Clopper-Pearson) methods for the proportion of each correct outcome among the entire PP population, with mitigations, overall and by subgroups. The Overall Correct Final Use Outcome will also be evaluated without mitigations and with only *a priori* mitigations on the PP population overall and by subgroups.

An additional exploratory analysis of the Overall Correct Final Use Outcome, with *a priori* and post-study mitigations, will be performed on the PP population for those participants who had both a participant and CMOG final use assessment obtained solely from the Web App. The PE of the Overall Correct Final Use Outcome, with *a priori* and post-study mitigations, will be reported with a two-sided 95% confidence interval which will be computed using exact binomial (Clopper-Pearson) methods for the proportion of each correct outcome among the entire PP population overall and by subgroups. Overall Correct Final Use Outcome obtained

solely from the Web App TASS assessments will also be evaluated without mitigations and with only *a priori* mitigations on the PP population overall and by subgroups.

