Scenario	Participant LDL-C		Participant Final TASS Outcome	SMT Required (Y/N)	SMT Obtained (Y/N)	LDL-C (v)* input by CMOG	CMOG TASS Outcome	Coded Outcome	Is there a potential for a priori mitigation “Missing LDL-C Retest”?
	Value 1 (1 st retest)	Value 2 (2 nd retest)							
8	IR (v)	NR	DNU Kickout Reason: Increase or No Decrease in LDL Cholesterol	N	-	IR (v) - Value 1	DNU Kickout Reason: Inadequate Decrease on Follow Up LDL Cholesterol Retest	DNU outcome coded to Missing due to lack of two verified IR LDL-C values to determine final outcome	No
9a	IR	AR	OK to Use	Y	Y	SMT	If SMT is IR: DNU Kickout Reason: Inadequate Decrease on Follow Up LDL Cholesterol Retest If SMT is NR: DNU Kickout Reason: Increase or No Decrease in LDL Cholesterol	DNU outcome for IR result coded to Missing due to lack of two verified IR LDL-C values to determine final outcome Otherwise, same as CMOG TASS Outcome	Yes

Scenario	Participant LDL-C		Participant Final TASS Outcome	SMT Required (Y/N)	SMT Obtained (Y/N)	LDL-C (v)* input by CMOG	CMOG TASS Outcome	Coded Outcome	Is there a potential for a priori mitigation “Missing LDL- C Retest”?
	Value 1 (1 st retest)	Value 2 (2 nd retest)							
							If SMT is AR: OK to Use or Ask a Doctor		
9b	IR	AR	OK to Use	Y	N	No verified retest can be entered	OK to Use	“OK to Use” outcome coded to Missing due to a missing verified LDL-C retest value	Yes
10	IR (v)	IR (v)	DN Kickout Reason: Inadequate Decrease on Follow Up LDL Cholesterol Retest	N	-	IR (v) - Value 2	DN Kickout Reason: Inadequate Decrease on Follow Up LDL Cholesterol Retest	Same as CMOG TASS Outcome	No
11	IR	IR	DN Kickout Reason: Inadequate Decrease on Follow Up LDL Cholesterol Retest	N	-	No verified retest can be entered	OK to Use	“OK to Use” outcome coded to Missing due to a missing verified LDL-C retest value	No

Scenario	Participant LDL-C		Participant Final TASS Outcome	SMT Required (Y/N)	SMT Obtained (Y/N)	LDL-C (v)* input by CMOG	CMOG TASS Outcome	Coded Outcome	Is there a potential for a priori mitigation “Missing LDL- C Retest”?
	Value 1 (1 st retest)	Value 2 (2 nd retest)							
12	IR	AR (v)	OK to Use	N	-	AR (v) - Value 2	OK to Use	Same as CMOG TASS Outcome	No
13	IR (v)	AR (v)	OK to Use	N	-	AR (v) - Value 2	OK to Use	Same as CMOG TASS Outcome	No
14	IR (v)	NR (v)	DNU Kickout Reason: Increase or No Decrease in LDL Cholesterol	N	-	N (v) - Value 2	DNU Kickout Reason: Increase or No Decrease in LDL Cholesterol	Same as CMOG TASS Outcome	No

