
Missing LDL-C Retests
 
 - Given consumers can only purchase non-prescription rosuvastatin through the Web App, we can stop shipping medication to individuals who fail to retest after a period of time agreed with FDA. Thus, for participants who qualify for treatment (i.e., have an “OK to Use” outcome or an “Ask a Doctor” outcome and indicates the doctor gave them permission to use the drug) but fail to obtain the necessary verified retest(s) (whether it is an initial retest or a second retest in those with an inadequate response), an a priori mitigation allowing these individuals to be mitigated to a “correct” response is appropriate. This mitigation can only be applied in situations where the CMOG’s outcome was “coded” as “missing” because of a missing LDL-C value, and the CMOG’s TASS outcome would have matched the Participant Outcome if not for the missing LDL-C retest. 	
 1. CMOG final TASS assessment is “OK to Use” or “Ask a Doctor”, but is coded as “Missing” because the participant failed to obtain a verified LDL-C retest or an SMT. 2. CMOG final TASS assessment is “OK to Use” but coded as “Missing” because the participant failed to retest and the SMT was an Inadequate Response, or the participant self-tested with a verified inadequate response result that was used for their Visit 2 reassessment. 3. Participant enters an initial Inadequate Response LDL-C retest into the Web App (verified or unverified), has an “OK to Use” outcome or “Ask a Doctor” outcome, indicates the doctor gave them permission to use the drug and makes a purchase. CMOG final TASS assessment is coded as “Missing” because only one or no verified LDL-C retest value was available for use, but otherwise would have matched the participant outcome. (Table XX, scenarios 1b, 2b, 3a, 3b, 4a, 4b, 7b, 9a, 9b)

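### The second co-primary's denominator sentence shuts out cases that the plan's own rules score as correct or incorrect; followed literally, it raises the rate

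*SAP*

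**What the plan says.** **Denominator.** SAP 4.2.2 (Final Use Assessment) states that the primary denominator "will only include those participants in the analysis population with a non-missing final use outcome for the participant and CMOG". SAP 1.3 has the same term in its formula: "Number of participants in the analysis population with a non-missing final use outcome for both the participant and CMOG". Protocol 9.4.2.1 defines the endpoint as the number with a correct outcome "divided by the number of participants in the analysis population with a non-missing final use outcome for both the participant and CMOG clinician". SAP 4.1.3 adds: "All primary analyses, except the first co-primary endpoint, will be conducted based on a complete case analysis".

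**Population.** SAP 4.2.2 also says that the primary analysis of this endpoint includes all PP participants. Both SAP 4.2.2 and protocol 9.4.2.1 place the exact interval among the entire PP population.

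**Numerator.** It is the sum of correct selectors, correct Ask a Doctor cases, correct rejectors, and all a priori and post-study mitigations. One a priori mitigation, Missing LDL-C Retests (protocol Table 6, SAP Appendix D), turns a case into a correct one. On its scope, Appendix D says: "This mitigation can only be applied in situations where the CMOG’s outcome was “coded” as “missing” because of a missing LDL-C value". SAP Appendix A, Table A1, marks nine scenarios as eligible (1b, 2b, 3a, 3b, 4a, 4b, 7b, 9a, 9b). In 9a the study mandated test was done, yet the coding for an inadequate response is: "DNU outcome for IR result coded to Missing due to lack of two verified IR LDL-C values to determine final outcome".

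**Stop Use cases found by the CMOG.** SAP 3.2.3.3 and 3.2.6 say that if such a participant never reordered, the participant's own final use outcome is missing and is not imputed. The overall result is nevertheless Incorrect. Protocol 8.1 says "they will be considered a failure when evaluating the second co-primary endpoint related to" use. SAP 3.1 gives the reason for scoring these cases Incorrect: "since the participant did not identify the condition and stop medication". SAP Appendix B lists them as PP and Incorrect when the history is sufficient.

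**The concern.** The denominator sentence does not fit either scoring rule.

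- Every success credited under Missing LDL-C Retests has, by the terms of that mitigation, a missing CMOG outcome. It enters the numerator but fails the denominator's condition.
- A CMOG-identified Stop Use case with no reorder is a prescribed failure, but its participant outcome is missing. The denominator removes it.

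Both errors push the rate up. A ratio in which some successes are not among the trials is not a binomial proportion, so the Clopper-Pearson interval that decides this co-primary would not be valid for it. The endpoint has a fixed pass line, a lower bound above 85%, so the denominator should not depend on which of two conflicting sentences the programmer follows.

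A related conflict is in SAP Appendix B. A participant in the study for more than 3 months without a verified LDL-C retest is listed as AUS ITT and Withdrawal, but the same row says the mitigation is possible. SAP 3.1 says that withdrawals have neither completed Virtual Visit 2 nor given enough data for a final use outcome, which puts them outside PP as SAP 2.1 defines it. A participant who did complete Virtual Visit 2 would be in PP under SAP 2.1.

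**Working it through.** **Inputs.** N = 500, true rate 90%, power at least 90%, and success if the lower bound (LB) of the two-sided 95% Clopper-Pearson interval exceeds 85% (SAP 1.3 and 4.2.2). The documents do not give the number of affected cases, so m and f below are assumptions.

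**The plan's own figure.** At n = 500 the smallest passing count is 441 (88.2%, LB 85.04%). With a true rate of 90% the power is 91.9%, which agrees with the stated figure. The sample size is not in question.

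**Notation.** Among scored PP participants:
- n = those with both outcomes non-missing, of whom c are correct;
- m = Missing-coded cases mitigated to correct;
- f = CMOG-identified Stop Use failures with a missing participant outcome.

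Literal rate = (c + m)/n. Rate with every scored participant counted = (c + m)/(n + m + f). The first divided by the second is (n + m + f)/n, which exceeds 1 whenever m + f > 0. The literal rate is not capped at 100%: c = 400, m = 60, n = 450 gives 460/450 = 102%.

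**Pass mark under the literal rule, 500 scored participants.** The last column takes total correct as Bin(500, 0.85) with m and f fixed.

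| m | f | n | correct or mitigated needed | as % of 500 | chance of passing if true rate is 85% |
|---|---|---|---|---|---|
| 0 | 0 | 500 | 441 | 88.2% | 2.3% |
| 0 | 2 | 498 | 440 | 88.0% | 3.2% |
| 10 | 0 | 490 | 433 | 86.6% | 17.4% |
| 20 | 0 | 480 | 424 | 84.8% | 58.0% |

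**One data set, two denominators.** Take 440 correct or mitigated among 500 scored.
- All counted: 440/500 = 88.0%, LB 84.82%, fails.
- Literal, m = 10, f = 0: 440/490 = 89.8%, LB 86.77%, passes.
- Literal, m = 0, f = 2: 440/498 = 88.4%, LB 85.21%, passes.

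At the threshold itself one failure is enough: 441/500 passes (LB 85.04%) and 441/501 fails (LB 84.85%).

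**At the planning value.** 450/500 has LB 87.03%. It would take 11 restored failures to reverse that verdict (450/510, LB 85.12%; 450/511, LB 84.93%). Leaving the mitigated cases out of both parts also passes: 430/480 at m = 20 (LB 86.50%) and 410/460 at m = 40 (LB 85.92%).

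**The case against.** The strongest reply is that the plan already shows who belongs in the denominator. SAP 4.2.2 says all PP participants are in the primary analysis and places the interval among the entire PP population. The 3×3 figure puts mitigated cases in the diagonal cells. Four places (protocol 8.1; SAP 3.2.3.3, 3.2.6 and Appendix B) score the Stop Use cases Incorrect. A careful programmer would read the denominator sentence in that light, and a ratio above 100% would be noticed. Most of this stands: the intended rule can be inferred, and the Stop Use group is narrow. But the sentence that limits the denominator appears in three places, SAP 4.1.3 supports it by calling the analysis complete case, and nothing says that mitigation removes the Missing code. The result is a contradiction in the current text. A reader might infer that the plan is silent on the point; it is not.

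A reader might also take leaving the Missing-LDL-C cases out of both parts as an equally good reading, under which the rate can fall (430/490 = 87.8% against 440/500 = 88.0%). The documents do not support that. The mitigation applies only to Missing-coded cases, so it could then never affect the primary rate, although the primary estimate is defined with a priori mitigations.

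Nor does the gap between at least 500 evaluable here and at least 450 for the LDL-C endpoint bound m. The first figure is for PP and the second for AUS ITT, and several eligible scenarios (1b, 2b, 3a, 4a, 7b, 9a) do have a verified LDL-C.

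Finally, SAP 4.2.2 plans results without mitigations and with a priori mitigations only, a table of counts for each mitigation, and best-case, worst-case and tipping-point analyses. The table should show m. None of these defines the primary rate.

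**Conclusion.** The denominator as written is wrong: it contradicts the scoring rules and the statement that all PP participants are analysed. The upward direction follows from algebra, given that the numerator keeps the mitigated cases as the formula states. The size is conditional. With 500 scored participants, the literal rule lowers the pass mark from 441 to 433 at m = 10 and to 424 at m = 20, but m and f are plain assumptions and f is probably small. At the planned 450 of 500 the verdict does not change; the choice matters mainly for a result near the 85% bound. A reader might infer that this co-primary's result will be wrong. The documents do not support that, because they give no counts and the intended rule can be inferred. The point should be fixed, and it does not affect the sample size or power.

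**What to change.** - In protocol 9.4.2.1 and SAP 1.3 and 4.2.2, define the denominator as every PP participant with an assigned overall final use result: correct, mitigated or incorrect. State that Missing-LDL-C mitigated cases count in both numerator and denominator, and that CMOG-identified Stop Use cases count in the denominator as Incorrect even when the participant outcome is missing. Align the complete-case wording in SAP 4.1.3.
- Reconcile the Appendix B row for more than 3 months without a verified LDL-C with SAP 2.1 and 3.1. Either the case is in PP and can be mitigated, or it is a withdrawal and cannot.
- Optionally, add one sensitivity line that leaves the Missing-LDL-C cases out of both parts. The planned table for each mitigation already gives their number.

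The cost is one sentence in three places with a matching edit to SAP 4.1.3, one table row, one programming rule and, if wanted, one output line. No new data are needed. The reported rate may be slightly less favourable than under the literal wording.
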